## 1.0 PROTOCOL SUMMARY AND/OR SCHEMA

This is a phase II study evaluating the efficacy of nivolumab in combination with ipilimumab in patients with recurrent and/or metastatic (R/M) salivary gland cancers (SGCs). Patients will be enrolled to two cohorts: Cohort 1, patients with R/M adenoid cystic carcinoma (“ACC group”), and Cohort 2: patients with R/M SGC of any histology, except ACC (“non-ACC group”). Patients will be required to have RECIST v1.1 measurable disease, any number of prior therapies, and no previous exposure to immunotherapeutic approaches. For the ACC cohort, patients with non-salivary primary sites would be allowed.

The primary endpoint for the study is best overall response rate (BOR = CR+PR) documented by RECIST v1.1 criteria. Secondary endpoints are progression-free survival (PFS) and safety/tolerability of the drug combination. These endpoints will be evaluated in each cohort separately. An exploratory endpoint is to analyze tumor tissue and peripheral blood cell subsets for potential biologic correlates of immune activation and efficacy with combination therapy.

Enrolled patients will be treated with nivolumab 3 mg/kg every 2 weeks plus ipilimumab 1 mg/kg every 6 weeks (1 cycle= 6 weeks). RECIST v1.1 response assessment will be at baseline and then approximately every 12 weeks (+/- 1 week) (or approximately every 2 cycles of combination treatment). Given the potential for delayed responses following short periods of disease progression, subjects may continue to receive therapy beyond radiographic progression in the absence of clinical deterioration and after discussion with the Principal Investigator. Patients will be continued on therapy until disease progression, unacceptable toxicity, patient withdrawal of consent, or investigator’s discretion. Adverse events will be monitored from the start of therapy until 30 days after the last dose of drug.

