### **Secondary Objective**

To determine the progression-free survival (PFS) of patients with recurrent/metastatic SGC treated with nivolumab and ipilimumab.

To determine the safety/tolerability of nivolumab and ipilimumab in patients with recurrent/metastatic SGC.

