*Rationale for the nivolumab 3 mg/kg every two weeks plus ipilimumab 1 mg/kg every 6 weeks dose/schedule:* The FDA approved dose/schedule for unresectable or metastatic melanoma is nivolumab 1 mg/kg plus ipilimumab 3 mg/kg every three weeks for 4 combined doses, followed by nivolumab 3 mg/kg every two weeks alone. CheckMate-012 was an open-label, phase I multicohort trial evaluating the safety and efficacy of nivolumab alone and in combination with a variety of agents, including nivolumab plus ipilimumab, for first-line treatment of Stage IIIB/IV non-small cell lung cancer (NSCLC) patients. The nivolumab/ipilimumab regimens initially evaluated included the FDA approved schedule for melanoma as well as nivolumab 3 mg/kg plus ipilimumab 1 mg/kg every 3 weeks for 4 combined doses, followed by nivolumab 3 mg/kg every two weeks alone. However, both of these schedules were deemed poorly tolerated with 25/49 patients (51%) developing Grade 3/4 treatment-related AEs, three treatment-related deaths, and a 33% discontinuation rate for Grade 3/4 treatment-related AEs. As a result, four additional cohorts were introduced to the trial for evaluation: nivolumab 1 mg/kg plus ipilimumab 1 mg/kg every 3 weeks for 4 cycles, nivolumab 1 mg/kg every 2 weeks plus ipilimumab 1 mg/kg every 6 weeks, nivolumab 3 mg/kg plus ipilimumab 1 mg/kg every 12 weeks, and nivolumab 3 mg/kg every 2 weeks plus ipilimumab 1 mg/kg every 6 weeks. While each of these regimens were deemed to be better tolerated than the initial two schedules tested, the nivolumab 1 mg/kg dosing was associated with less clinical activity. Hence, only the safety and efficacy profiles observed with nivolumab 3 mg/kg plus ipilimumab 1 mg/kg every 6 weeks or every 12 weeks were deemed promising for further clinical development. The nivolumab 3 mg/kg every 2 weeks plus ipilimumab 1 mg/kg every 6 weeks was evaluated in 39 patients. Among those 39 patients, 28 (72%) had AEs of any grade; 13 (33%) developed Grade 3/4 treatment-related AEs. Five (13%) patients discontinued therapy due to treatment-related AEs. No treatment-related deaths were observed as of February 28, 2016. Promising activity was also observed with this regimen as 15 (38%) patients developed partial responses. The nivolumab 3 mg/kg and ipilimumab 1 mg/kg every 12 week cohort (n=38 patients) had comparable safety and a slightly higher rate of response (18 (47%) partial responses) to the ipilimumab every 6 week cohort. Notably, the study was not powered to formally compare safety or efficacy outcomes amongst the cohorts, and the slightly higher response rate in the ipilimumab every 12 week group may have been attributed to clinical imbalances within the small sample sizes treated in each cohort. Given the promising safety/efficacy profile and the hypothesis that greater ipilimumab exposure may be associated with greater clinical activity, the nivolumab 3 mg/kg every 2 weeks plus ipilimumab 1 mg/kg every 6 weeks was selected for evaluation in this phase II trial for R/M SGC population.

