stage can be made. In this case the study becomes a single-stage design in effect, which has the same type-I error rate, power, and rejection criterion for the null hypothesis as the original minimax two-stage design.

Patients who receive at least one dose of either study medication (nivolumab or ipilimumab) will be included in the evaluation of the primary objective. Patients who are enrolled, but withdraw consent or are removed from the study prior to obtaining the first response assessment while on study treatment can be replaced, except for those who were taken off study for progression of disease or toxicity (in these specific incidences, patients will be classified as non-responders).

Secondary endpoints will include measuring progression-free survival (PFS) with recurrent/metastatic SGC treated with nivolumab and ipilimumab, and assessing the safety/tolerability of the regimen.

PFS will be estimated using Kaplan-Meier methodology, with time origin at the start of the treatment. Patients will be followed until progression of disease or death related to disease, whichever come first. Patients removed from the study for reasons unrelated to the disease (e.g. moving, accidental death) will be counted as censored. Patients who continue treatment beyond initial investigator-assessed, RECIST 1.1-defined progression, and are subsequently removed from study within the next radiographic assessment for progression, will be considered to have investigator-assessed progressive disease at the time of the initial progression event.

Safety will be assessed in terms of AEs, laboratory data and vital sign data, which will be collected for all patients. Appropriate summaries of these data will be presented. AEs will be listed individually per patient according to CTCAE version 4.0, and the number of patients experiencing each AE will be summarized. The safety population will comprise all patients who receive at least one dose of study treatment.

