### **17.2.1 SAE Reporting to BMS**

See Appendix 2 for Mandatory Adverse Event reporting information to be included in Investigator Sponsored Research protocols.

All Serious Adverse Events must be reported to BMS Worldwide Safety.

Following the subject's written consent to participate in the study, all SAEs, whether related or not related to study drug, must be collected, including those thought to be associated with protocol-specified procedures. All SAEs must be collected that occur within 100 days of discontinuation of dosing.

All SAEs must be collected that occur during the screening period. If applicable, SAEs must be collected that relate to any protocol-specified procedure (eg, a follow-up skin biopsy). The investigator should report any SAE that occurs after these time periods that is believed to be related to study drug or protocol-specified procedure.

SAEs, whether related or not related to study drug, and pregnancies must be reported to BMS within 24 hours. SAEs must be recorded on BMS or an approved form; pregnancies on a Pregnancy Surveillance Form.

**SAE Email Address:** [contact]

**SAE [contact]

If only limited information is initially available, follow-up reports are required. (Note: Follow-up SAE reports should include the same investigator term(s) initially reported.)

If an ongoing SAE changes in its intensity or relationship to study drug or if new information becomes available, a follow-up SAE report should be sent within 24 hours to the BMS (or designee) using the same procedure used for transmitting the initial SAE report.

All SAEs should be followed to resolution or stabilization.

The Sponsor/Investigator will ensure that all SAEs in the clinical database are reported to BMS and any applicable health authority during the conduct of the study. This reconciliation will occur at least quarterly and be initiated by the sponsor/investigator. Sponsor/investigator will request a reconciliation report from: [[contact]](mailto:[contact]). During reconciliation, any events found to not be reported previously to BMS must be sent to [[contact]](mailto:[contact]).

BMS SAE forms should be used, or if performed under a US IND a Medwatch or CIOMS form can be used as required by regulatory authorities..

Site specific forms will be requested for review.

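### The PFS rule counts only disease-related deaths as events and censors other deaths, so the reported curve can only equal or exceed true progression-free survival

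*Combined protocol and SAP*

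**What the plan says.** PFS is a secondary endpoint. Section 1.0 states "Secondary endpoints are progression-free survival (PFS) and safety/tolerability of the drug combination" and adds "These endpoints will be evaluated in each cohort separately"; Section 4.1 repeats this, and Section 2.0 lists PFS as a secondary objective. None of these places defines the event.

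The rule is in Section 14.0. The estimator is given as "PFS will be estimated using Kaplan-Meier methodology, with time origin at the start of the treatment". The end of follow-up is given as "Patients will be followed until progression of disease or death related to disease, whichever come first". The censoring rule follows: "Patients removed from the study for reasons unrelated to the disease (e.g. moving, accidental death) will be counted as censored".

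No part of the document counts death from any cause as a PFS event. Treatment-related death is named neither as an event nor as a censoring reason.

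**The concern.** An endpoint called progression-free survival should fail a patient who progresses or dies. Under Section 14.0 a death fails the patient only if it is judged related to the disease, and one kind of unrelated death is expressly censored. Two things follow.

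- **The estimate is not what its name says.** Censoring a death makes Kaplan-Meier behave as if the patient remained at risk of progressing later. The result is not the proportion alive and progression-free.
- **The estimate depends on attribution.** Each death before progression needs a disease or not-disease judgement in a single-arm, open-label study. Section 14.0 does not say who makes it or by what criteria. The deaths most relevant to the regimen, those from toxicity, fall in the gap: read literally they are not disease-related and so are not events.

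At stake is the PFS figure reported for each cohort. No hypothesis, threshold or comparator is attached to PFS, so the response-rate rule, sample size, type I error and power do not depend on it.

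**Working it through.** The plan states no PFS median, rate or event count, so there is no figure to reproduce. The check has two parts: direction, which is exact, and size, which needs assumptions.

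**Direction.** The Kaplan-Meier estimate is S(t) = ∏(1 − dᵢ/nᵢ) over event times up to t, with dᵢ events among nᵢ at risk. Recoding a death from event to censored at the same time leaves every nᵢ unchanged and can only lower dᵢ. Each factor stays the same or rises, so S(t) stays the same or rises at every t. In 20,000 simulated cohorts of 32, half with tied times, the curve under the plan's rule never fell below the all-cause curve and was strictly higher at some time in 16,472.

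**What the document offers on the rate of such deaths.** It gives none for salivary gland cancer. Section 3.0 gives treatment-related deaths elsewhere:

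- This regimen in lung cancer, 39 patients: "No treatment-related deaths were observed as of February 28, 2016". The one-sided 95% upper bound is 1 − 0.05^(1/39) = 0.074, and 0.074 × 32 = 2.4 patients.
- Pooled melanoma data, another schedule: 2/407 = 0.5%, or 0.16 per 32.
- The two initial lung cancer schedules, described as poorly tolerated: 3/49 = 6.1%, or 2.0 per 32.

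Accidental and intercurrent deaths would add to these; the document gives no rate for them.

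**Size, under assumptions.** Cohort size is 32 (Section 14.0). Assumed: constant hazards; a median m of 4 or 12 months when only progression and disease-related death count; k = 1 or 2 other deaths before progression within 12 months.

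1. Disease hazard: λd = ln 2 / m, which is 0.1733 per month for m = 4 and 0.0578 for m = 12.
2. Other-death hazard λo solves [λo/(λo + λd)] × [1 − exp(−12(λo + λd))] = k/32.
3. Excess at t: exp(−tλd) − exp(−t(λd + λo)).
4. All-cause median: ln 2 / (λd + λo).

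| m (months) | k | λo per month | Excess at 6 months (points) | Excess at 12 months (points) | All-cause median (months) |
|---|---|---|---|---|---|
| 4 | 1 | 0.0064 | 35.36 − 34.03 = 1.3 | 12.50 − 11.58 = 0.9 | 3.9 |
| 4 | 2 | 0.0130 | 35.36 − 32.69 = 2.7 | 12.50 − 10.69 = 1.8 | 3.7 |
| 12 | 1 | 0.0037 | 70.71 − 69.17 = 1.5 | 50.00 − 47.84 = 2.2 | 11.3 |
| 12 | 2 | 0.0075 | 70.71 − 67.59 = 3.1 | 50.00 − 45.69 = 4.3 | 10.6 |

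With k = 0 every excess is zero. Simulating 20,000 cohorts of 32 per setting, with no other censoring, gave mean 6-month differences of 1.30 and 1.56 points for k = 1 and 2.68 and 3.12 for k = 2 (m = 4 and 12), none below zero.

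**Scale.** The approximate 95% half-width of a 6-month estimate is 1.96 × √(p(1 − p)/32): 16.6 points at p = 0.354 (m = 4) and 15.8 points at p = 0.707 (m = 12).

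**The case against.** The strongest reply is that little turns on this. PFS is descriptive, no decision rests on it, and the assumed excess is a fraction of the sampling error. One or two such deaths per 32 is not a documented expectation: this regimen showed none in 39, and the pooled melanoma rate implies 0.16 per 32. All of that is right. It limits the importance of the point but does not make the rule correct. Unlike sampling error, this error has one direction, and the confidence interval does not reflect it.

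A second reply is that the leading sentence describes follow-up rather than events, and that toxic death is simply unaddressed. For response, Section 14.0 does class patients taken off for toxicity before their first assessment as non-responders. This stands in part: the handling of toxic deaths is an ambiguity, and treating them as non-events is only the literal reading. The core does not depend on it, because accidental death is expressly censored.

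A third reply is that the rule is stated openly and nothing in the document contradicts it, so the dispute is about a label. But the label is what readers will rely on, and no other section supplies an all-cause definition. With no comparator, attribution cannot bias a between-arm contrast, but it still moves the single-arm estimate.

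**Conclusion.** The concern holds: the rule is wrong as written for an endpoint named progression-free survival. The direction is exact, given the same times and other censoring. The size is unknown. It is zero if no non-disease death precedes progression. Under the assumptions above, one or two such deaths per cohort inflate 6-month PFS by 1.3 to 3.1 points and 12-month PFS by 0.9 to 4.3 points; a reported median of 12.0 months would be 11.3 or 10.6 counting all deaths, and a reported 4.0 would be 3.9 or 3.7. This is a mislabelled endpoint with a small expected numerical effect. It should be fixed, but it does not touch the primary analysis.

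**What to change.** In Section 14.0:

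- Define the PFS event as the first RECIST 1.1 progression or death from any cause, measured from the start of treatment.
- Remove accidental death from the censoring examples.
- If the present version is wanted, keep it as a sensitivity analysis under a name such as time to progression or disease-related death.

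As a separate clarification, Section 14.0 could state how removal for toxicity and the start of new anticancer therapy are handled for PFS, and how long deaths are sought after a patient leaves without progression.

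The cost is a change to two sentences and some data collection. Section 17.2.1 already requires "All SAEs must be collected that occur within 100 days of discontinuation of dosing", which captures deaths in that window; Section 17.2 sets 30 days for institutional reporting. The Section 10.0 schedule ends with the off-study evaluation, so later deaths may need chart review. Reported PFS may be slightly less favourable. Sample size and the response-rate design do not change.

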progression. The durable tumor regressions produced by agents that target this pathway in isolation provide the proof of principle that selective inhibition of T cell checkpoints can be an effective therapeutic strategy.

Recently, Mukaigawa et. al. reported that among a Japanese series of 219 surgically resected SGC tumors in the absence of metastatic disease, 22.8% expressed PD-L1 by immunohistochemistry (IHC), which was independently associated with poor disease-free survival. The extent of PD-L1 positivity varied amongst tumor histologies, with expression most frequently detected in large cell carcinoma, SDC, adenocarcinoma NOS, carcinoma ex pleomorphic adenoma, and squamous cell carcinoma. At the 2016 ASCO Annual Meeting, Cohen and colleagues presented the preliminary results for a cohort of PD-L1 positive, unresectable/metastatic SGC patients treated on a phase 1b trial with the PD-1 targeting antibody pembrolizumab (Merck; KEYNOTE-028). Among 26 evaluable patients, three partial responses (11.5%) and a 31% rate of tumor regression were observed. This preliminary data indicates that targeting PD-1 may have modest activity for a subset of SGC patients, and also suggests the hypothesis that combining PD-1 pathway blockade with other immune checkpoint inhibitors may further augment T-cell activation to enhance clinical efficacy.

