Target lesions. All measurable lesions up to a maximum of 2 lesions per organ and 5 lesions in total, representative of all involved organs, should be identified as **target lesions** and recorded and measured at baseline. Target lesions should be selected on the basis of their size (lesions with the longest diameter), be representative of all involved organs, but in addition should be those that lend themselves to reproducible repeated measurements. It may be the case that, on occasion, the largest lesion does not lend itself to reproducible measurement in which circumstance the next largest lesion which can be measured reproducibly should be selected. A sum of the diameters (longest for non-nodal lesions, short axis for nodal lesions) for all target lesions will be calculated and reported as the baseline sum diameters. If lymph nodes are to be included in the sum, then only the short axis is added into the sum. The baseline sum diameters will be used as reference to further characterize any objective tumor regression in the measurable dimension of the disease.

Non-target lesions. All other lesions (or sites of disease) including any measurable lesions over and above the 5 target lesions should be identified as **non-target lesions** and should also be recorded at baseline. Measurements of these lesions are not required, but the presence, absence, or in rare cases unequivocal progression of each should be noted throughout follow-up.

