#### **14.0 BIOSTATISTICS**

The primary endpoint of the study for each cohort is best overall response rate (BOR; CR+PR by RECIST v1.1). The ACC (Cohort 1) and non-ACC cohorts (Cohort 2) will be assessed separately. For ACC, our recent literature review of all systemic chemotherapy studies reported for R/M ACC patients from 1966 to 2009 revealed that these were generally small studies of variable, poor methodological quality from which definitive conclusions regarding the efficacy of chemotherapy are impossible to establish. Objective responses with cytotoxic chemotherapy were infrequent, and in 10 studies evaluating different targeted agents (imatinib, gefitinib, cetuximab, lapatinib, bortezomib (excluding the VEGR targeted TKIs)) involving 157 ACC patients, only 2 objective responses were reported (in response to high dose imatinib). Notably, there is no data addressing potential efficacy of systemic therapy beyond the first line setting in R/M ACC. The same concerns regarding trial design and modest activity with chemotherapy apply to non-ACC histologies as well. There currently is no standard therapy for SGs. Therefore, we will adopt a BOR of 5% as the null hypothesis and a BOR of 20% as desirable. A minimax two-stage design will be used for each cohort. In order to detect a difference between an unacceptable ORR of 5% and a desirable ORR of 20% with a one-sided type I error of 10% and power of 90%, at least 1 response needs to be observed among the first 18 patients enrolled in the first stage. If this is achieved, then the study will progress to the second stage in which an additional 14 patients will be accrued. In order to move to the second stage of the study, the patient response in the first stage must occur within 6 cycles (or 36 weeks (+/- 2 weeks)) of drug treatment. At the end of the trial, at least 4 responses need to be observed among a total of 32 patients of the cohort to be considered worthy of further investigation. Maximum number of patients treated in both cohorts combined would be 64 patients.

Given the length of the observation period for response, if the decision on whether to proceed to the second stage cannot be made after the first 18 patients have been enrolled, the study will not halt and patients will continue to be enrolled. In the worst case scenario, all 32 patients will have been enrolled before the decision on whether to proceed to the second

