Due to the limited sample size, the analyses investigating the association between correlative markers and BOR will be exploratory. These exploratory analyses will be evaluated within each cohort separately. Categorical markers will be correlated with BOR by Fisher's exact tests. Continuous markers will be correlated with BOR by logistic regression. Immune activation that occurs concomitant with experimental therapy will be serially assessed in the PBMC analysis performed for each patient. Specifically, the changes in T cell subsets that occur with therapy will be analyzed and interpreted as potential indicators of immune activation induced by drug therapy. Proportions of T cell subsets will be calculated with 95% confidence intervals at each time point and plotted over time to reveal any trend. The baseline proportions of T cell subset and changes in these proportions from baseline to last time point will be correlated with the response status univariately.

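### All marker-versus-efficacy tests use binary response, so they give no information in a cohort without responders; percent change in tumor size should be prespecified as a companion measure

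*Combined protocol and SAP*

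**What the plan says.** Section 2.0 sets the exploratory objective as finding biologic correlates of efficacy in tumor tissue and peripheral blood. Section 14.0 then says: "Due to the limited sample size, the analyses investigating the association between correlative markers and BOR will be exploratory". It plans Fisher's exact tests of categorical markers against BOR, logistic regression of BOR on continuous markers, and univariate correlation of T-cell subsets (baseline and change) with response status, all within each cohort. The same section defines BOR as CR+PR, and Sections 10.0 and 12.4.3 call for confirmation. PFS is a secondary endpoint estimated by Kaplan-Meier and is not linked to markers.

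On early stopping, Section 14.0 requires that "at least 1 response needs to be observed among the first 18 patients enrolled in the first stage"; for a positive result, "at least 4 responses need to be observed among a total of 32 patients of the cohort". Enrolment does not halt while the stage 1 decision is pending.

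On tumor size, Section 12.2 says: "The baseline sum diameters will be used as reference to further characterize any objective tumor regression in the measurable dimension of the disease". Follow-up sums are not described there, but Section 12.4.1 needs them to classify PR and PD. Section 14.0 makes no use of the change in these sums.

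**The concern.** The objective is efficacy, but the only efficacy measure offered to the markers is a yes/no outcome that is expected to be rare. A patient with 29% shrinkage is scored the same as one who progresses at the first scan. The stopping rule makes this worse: a cohort that stops at stage 1 has, among its 18 stage 1 patients, an outcome with no variation, and the plan names no alternative. Patients are asked for two research biopsies (with listed exemptions) and serial blood, partly to answer this question. If tumor-size change is picked up only after a cohort shows no responders, the outcome has been chosen after seeing the data.

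The background hints that shrinkage is more common than response in this disease. In the cited PD-1 antibody study of 26 evaluable PD-L1-positive patients, "three partial responses (11.5%) and a 31% rate of tumor regression were observed". That shows more variation to work with; it says nothing about whether any marker tracks it.

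**Working it through.** **Inputs (Section 14.0).** "we will adopt a BOR of 5% as the null hypothesis and a BOR of 20% as desirable"; one-sided type I error 10%, power 90%; 18 patients then 14 more, 32 in total; continue with at least 1 response; success with at least 4.

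**1. Reproduce the design.** P(success) = sum over x = 1 to 18 of Bin(x; 18, p) × P[Bin(14, p) ≥ 4 − x].
- p = 5%: 7.2%, within the 10% bound.
- p = 20%: 90.1%.

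The stated design reproduces, so the stopping rule can be taken as written.

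**2. Chance of no responders,** (1 − p)^n.

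| True rate | 0 of 18 | 0 of 32 |
|---|---|---|
| 5% | 0.95^18 = 39.7% | 0.95^32 = 19.4% |
| 10% | 0.90^18 = 15.0% | 3.4% |
| 11.5% (PR rate in the cited study) | 0.885^18 = 11.1% | 2.0% |
| 20% | 0.80^18 = 1.8% | 0.1% |

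The second column applies if enrolment runs on to 32 before the decision. At 5% with 32 enrolled, P(0 or 1 responder) = 0.95^32 + 32 × 0.05 × 0.95^31 = 0.194 + 0.326 = 52%.

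**3. What the planned tests return.** With no responders, Fisher's p is 1 for any marker and the logistic fit has no finite estimate. With k responders among 32 and a marker split 16/16, the most extreme table puts all k on one side, so the smallest two-sided Fisher p is 2 × C(16,k)/C(32,k):
- k = 1: 1.0
- k = 3: 2 × 560/4,960 = 0.23
- k = 4: 2 × 1,820/35,960 = 0.10
- k = 5: 2 × 4,368/201,376 = 0.043

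So at the success threshold of 4, an evenly split marker that captured every responder could not reach 0.05.

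**4. Power with tumor-size change (simulation).** Assumptions, none from the documents: marker and depth of response bivariate normal, correlation 0.4 to 0.5, n = 32, response defined as the deepest 12.5% or 20%, two-sided 5%.
- Spearman on percent change, every patient with a usable value: about 58% at correlation 0.4, 77-80% at 0.5.
- Planned logistic regression on response (likelihood-ratio test): about 33% at the low end of these settings, 47-53% at correlation 0.5.

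**5. Effect of a worst-rank rule at correlation 0.5.** If 20% of patients get the worst rank, Spearman power falls to 54-57% when they are drawn at random from non-responders, and to 68-72% when drawn from the half with the poorer tumor change. With 35% at random it is 36-44%, below the logistic regression. At correlation 0.4 with 20% at random it is 35-38%, against 32-39%: no clear gain.

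**The case against.** The strongest reply is that the plan already calls these analyses exploratory because of sample size, that no decision, error rate or sample size depends on them, and that nothing bars further exploratory work. That stands, and it keeps this a minor point. But the label excuses low power; it does not supply an analysis when the outcome is constant.

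A reader might infer four stronger things that the documents do not support.

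- **That no marker work is possible without responders, so the samples are wasted.** Section 14.0 also plans T-cell subset proportions with 95% confidence intervals over time, and Section 9.4 plans comparison of pre- and post-treatment biopsies. Neither needs a responder. Only the link to efficacy fails.
- **That a 40% failure rate is the expected case.** It holds at a true rate of 5% with 18 patients. If the 2-3 patients a month in Section 7.0 split equally between cohorts (an assumption), some 8-12 more per cohort enter during the 36-week window, giving 26-30 patients and P(no responder) = 0.95^30 to 0.95^26, or 21-26%, at 5%.
- **That tumor-size data are discarded.** They are collected for RECIST; they are only unused for the markers.
- **That percent change should replace BOR as the main measure.** That is a trade-off. It would separate the marker results from the primary endpoint, and best percent change ignores duration: a patient stable for two years at 0% gains nothing. In ACC, which Section 3.0 says is often indolent at first, small changes may not reflect drug effect. Adding a measure avoids this trade-off.

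The power gain is also not assured. The first scan comes at about 12 weeks, and Section 3.0 describes SDC and other subtypes as more uniformly aggressive, so the share needing a worst rank could be substantial. Reading BOR as four categories would let Fisher's test run without responders, but Section 14.0 defines BOR as CR+PR and pairs it with logistic regression.

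**Conclusion.** The point holds as a gap in the exploratory plan. Every marker-efficacy test rests on binary response within cohort. In a cohort with no responders (39.7% for 18 patients at a 5% rate, 15.0% at 10%, 11.1% at 11.5%, 1.8% at 20%; 19.4% for 32 patients at 5%) those tests carry no information, and with 4 of 32 an evenly split marker cannot go below p = 0.10. These figures follow exactly from the plan's rules, given the true rate.

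The power advantage of tumor-size change, about 58-80% against about 33-53%, rests on assumed correlations, normality and a usable value for every patient. It shrinks, and may nearly vanish, once about 20% or more of patients need a worst rank. The firmer argument is that percent change still varies when nobody responds. The primary analysis, its error rates and the sample size are unaffected.

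**What to change.** In Section 14.0 keep the BOR analyses and add a prespecified companion efficacy measure for the markers in each cohort: best percent change from baseline in the sum of target-lesion diameters, up to first RECIST progression. Use Spearman correlation for continuous markers and a rank-sum test for categorical ones.

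Give the worst rank to patients who progress only by new or non-target lesions, and to those who leave for progression or toxicity without a post-baseline scan. The second group is already classified as non-responders in Section 14.0. Report how many patients this covers, since the value of the measure depends on it.

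State that the companion measure carries the marker-efficacy analysis when a cohort has no or very few responders.

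Cost: one paragraph and no new data. Downside: one more exploratory analysis per marker, and a worst-rank convention that can dilute the association.
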